## SECTION 2. Assessment and Evaluation of the Risks

For details, refer to the UK IRB's [Policy on Children in Research](#).

A. Provide justification for the participation of children as research subjects in your study.

The purpose of the study is to assess the effects of an adapted evidence-based parenting intervention on parent behaviors, child behaviors, child adherence to wearing their hearing equipment, and child speech/language outcomes. For all four outcomes, participation of the children is needed in assessment of outcomes, including videotaped tasks, parent-report measures, and measures administered directly to children. Children's direct participation in the parenting intervention is not necessary.

B. Has this research been conducted in adults? ☒ Yes ☐ No

If yes, is there any indication that the proposed research would benefit, or at least not be harmful to children?

There are 40 years of research evidence demonstrating the benefits of evidence-based parenting interventions to children and families.

C. Indicate how many children you propose to enroll in the study:

**Note:** Whenever possible, involve the fewest number of children necessary to obtain statistically significant data which will contribute to a meaningful analysis relative to the purpose of the study.

Justify this number:

Two children have already participated in Aim 3, the piloting of trial procedures. We plan to enroll 125 parent-child dyads (125 parents, 125 children; 72 dyads randomized to the intervention and 53 dyads randomized to the control condition) in the effectiveness trial, Aim 4. This number was determined by our biostatistician based on the individually-randomized trial design,  $\alpha=.05$ , the potential of clustering at the interventionist level, and the need to detect a medium-sized effect on the primary outcome (parenting behaviors).

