#### AIM 4 (EFFECTIVENESS)

(1) Parents/Caregivers and Children: In Aim 4, research staff trained in human subjects protection will conduct the process of informed consent with each parent/caregiver participant prior to initiating study procedures. The parents/caregivers will provide written informed consent for themselves and on behalf of the child participants who are ages 3-6 during enrollment. A trained research staff member will review eligibility and all required elements of informed consent timepoint during the recruitment phone call, assuring that all of the parent's questions are answered. When the parent expresses interest in the study, the informed consent document will be sent either via email (using the E-Consent Framework in REDCap – see REDCap screenshots) or with a paper copy by mail if requested. Parents will be provided with phone and email contact information for the research team if they have any additional questions when reviewing the informed consent document. If consent is documented via the online REDCap instrument, a PDF of the signed version will be automatically emailed to the participant. If the consent form is mailed, an additional paper copy will be provided to the participant, along with a stamped envelope to return the signed copy. Receipt of any signed informed consent documents received by mail will be documented in REDCap. No assessment forms or other research material will be collected from the participant until the signed informed consent document is obtained. The signed paper consent documents will be separated from the data forms when filed in the research office. Electronic copies will be stored in REDCap.

Active study participants who signed informed consent prior to the July 2022 IRB modification that changed to all remote data collection procedures (vs. the previous protocol for conducting in-person language assessments with children at 12-, 24-, and 36-mo assessments), will be re-consented and will sign the updated IRB-approved consent form. Trained research staff members will contact each of these participants (n=32), explain the changes, review all required elements of informed consent, and send the informed consent document using the same methods above (i.e., either an emailed link via REDCap, or by mail if preferred by the participant). Signed copies of both the original and the updated consent forms will be kept on file for these participants. New participants will sign the updated consent form.

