This pattern will continue (annual assessment for all participants + FCU-DHH sessions for FCU-DHH participants only, follow-up six months later for all participants) up to a maximum of 36 months after baseline, or until the study ends (participants enrolling after the 3/2/2023 IRB modification/approval are anticipated to end participation after the 18-month assessment). All data collection will occur remotely. This includes full (i.e. "annual") parent and child assessments at baseline (including child assessments of speech, language, and hearing for participants enrolled after the 3/2/2023 IRB modification/approval), 12-month, 24-month and 36-month follow-ups for all participants; reduced (i.e., "mid-year") parent-only assessments at 6-month, 18-month, 30-month follow-ups for all participants; and FCU-DHH sessions for only FCU-DHH participants following the baseline, 12-month, and 24-month assessments). All parents/caregivers will be compensated \$75 following the baseline assessments before 3/2/2023 (which do not include child language measures); \$100 for baseline assessments after 3/2/2023 (including child language measures) and each annual assessment, and \$50 for completing each mid-year assessment. With parental permission, each child will be allowed to select a small age-appropriate toy (stuffed animal, book, puzzle, etc.) following their participation in annual assessments to acknowledge their contribution to the study. No compensation will be provided for participation in the FCU-DHH sessions. This strategy is intended to make the intervention itself as similar as possible to what it would be if offered outside of a research protocol. At the completion of the study, Aim 4 parent participants will receive an additional payment of \$100 if all 7 sets of research assessments are completed, an additional \$75 if 6 sets of assessments are completed, an additional \$50 if 5 sets of assessments are completed, and an additional \$25 if 4 sets of assessments are completed. These amounts are intended to compensate parents for their long-term participation and keep parents engaged even if some assessments are missed.

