At each six-month follow-up assessment (i.e., 6 months, 18 months, 30 months), a subset of these parent measures will be repeated, and the FCU-DHH participants will also complete the Therapy Attitude Inventory (TAI; satisfaction measure; 5 minutes). Parent-report language measures will not be administered at the six-month follow-up assessments to reduce participant burden (i.e., MacArthur-Bates, MAIS). There are also no videotaped FIT tasks at six-month follow-up assessments.

Description of child measures: At annual (12-month, 24-month, 36-month, and baseline for participants recruited after 3/2/2023) assessments, we will administer several key measures of child language development outcomes directly to children: the Ling sounds test (2 minutes); the CELF Preschool-3 (ages 3-6) or the CELF-5 (age 7 years and older; 30 minutes - different subtests used for children 7-8 years vs children 9 years and older); the PPVT-5 (15 minutes); and the BIT (5 minutes). The language assessment will be conducted by Zoom videoconferencing and will be recorded to assist in scoring the assessments per their established protocols. Children will participate in videotaped FIT tasks alongside their parent(s), as described above. Language measures will not be administered at the six-month follow-up assessments (i.e., 6-month, 18-month, 30-month).

Additionally, FCU-DHH participants will complete a 20-item set of questions that assesses their satisfaction with their interventionist (SWI - 5 minutes to complete). Each FCU-DHH participant will answer the SWI questions at the assessment timepoint that most closely aligns with the end of their involvement in the study (e.g., participants who enrolled in 2021 will complete these questions at their 36-month assessment; those who enrolled in 2023 will complete these questions at their 18-month assessment because study funding ends in May 2025). In comparison, the TAI assesses satisfaction with the intervention (not the interventionist) and is repeated at 6-month, 18-month, and 30-month assessments.

For all participants, the battery of measures (see Form M) is written at an 8th-grade reading level or below. Data collectors will be trained by the investigators ([name] for sociodemographic and behavioral measures; [name] for speech and language measures) in standardized protocols for administering these measures.

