Aim 4 data analyses: To make trial arm (FCU-DHH vs. TAU) comparisons, we will utilize linear mixed modeling. In the models, we will utilize random effects corresponding to the interventionists, thus accounting for the possibility of clustering of outcomes from parent-child dyads who received the intervention from the same person. For the analysis of our primary outcome (parenting behaviors as measured by PARYC score at the first 6-month follow-up), a fixed effect for trial arm (FCU-DHH vs. TAU) will be the primary covariate of interest. Additional analyses for Hypotheses 1-4 will address each outcome over time (i.e., PARYC scores as well as continuous measures of child behavior, parent-report and objective adherence with HA/CI, and language development). To account for the correlation among repeated measurements from the same subject, in addition to random effects corresponding to the interventionists, we will also utilize an unstructured within-subject covariance structure. In these multilevel models, trial arm, time (categorical), and their interaction will be used as predictors, with the interaction being of primary interest. All tests will be two-sided with a 5% significance level and will be conducted in SAS Version 9.4 or higher (SAS Institute, Cary, NC). Furthermore, analyses will be based on intention-to-treat.

Principal components analysis and z-scores may be used to create composite language outcomes at each time-point due to the multiple measures proposed, which may reflect a single common trait. 100 Note that because rolling study enrollment is necessary (especially in smaller clinics), some parent-child dyads may have fewer observations than others.

We will measure potentially important predictors (e.g., sex, race, parental age, socioeconomic status, degree of hearing impairment, type of hearing rehabilitation device, baseline language development), and statistically compare the balance of the two trial arms. Secondary analyses will include these variables as covariates within the previously described models.

Prior to analyses, we will inspect variable distributions using histograms, probability plots, and residual plots. If necessary, transformations will be performed to make the variable distributions approximate a normal distribution. Alternatively, generalized estimating equations (GEE) may be utilized.

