## Statistical Analysis Plan

All tests will be two-sided with a 5% significance level and will be conducted in SAS. Analysis methods will account for clustering within parent coaches (i.e., statistical correlation among the outcomes from participants who share the same interventionist). Therefore, analysis of our primary outcome (parenting behaviors as measured by PARYC score at the first 6-month follow-up) will be achieved with linear mixed-effects modeling, with random effects to account for this clustering. A fixed effect for trial arm (FCU-DHH vs. TAU) will be the primary covariate of interest. Additional analyses will address each outcome over time (i.e., PARYC scores, PARCHISY scores, measures of child behavior, parent report and objective adherence with HA/CI, and language development). In longitudinal analyses, linear mixed effects modeling will be adjusted to account for the additional level of correlation among outcomes from the same subject (e.g., a random time effect or an unstructured covariance). Fixed effects will include trial arm, time (categorical or continuous variable), and their interaction, with the interaction being of primary interest. Because rolling study enrollment is necessary, some parent–child dyads may have fewer observations than others. Recommended statistical approaches will be used for missing data within interventionists (e.g., multiple imputation at the subject and cluster level). Sensitivity analyses will be considered and dictated by the type of missing data. We will measure potentially important predictors (e.g., sex, race, parental age, socioeconomic status, degree of hearing loss, type of hearing rehabilitation device, and baseline language development) and statistically compare the balance of the two trial arms. Secondary analyses will include these variables as covariates. Stratified randomization (by device type and poverty level) will be accounted for in analyses.

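### No small-sample method is specified for the longitudinal arm-by-time tests; with only about 32 of 125 dyads able to reach month 36, an uncorrected seven-visit test would run at roughly 9-15% instead of 5%

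*Combined protocol and SAP*

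**What the plan says.** The protocol (Research Procedures, Aim 4 data analyses) makes PARYC at the first 6-month visit the primary analysis. The outcomes of Hypotheses 1-4 over time are additional analyses. For these it prescribes an unstructured within-subject covariance plus interventionist random effects, and: "In these multilevel models, trial arm, time (categorical), and their interaction will be used as predictors, with the interaction being of primary interest". The level is fixed: "All tests will be two-sided with a 5% significance level and will be conducted in SAS Version 9.4 or higher".

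The Statistical Analysis Plan repeats the level ("All tests will be two-sided with a 5% significance level and will be conducted in SAS") but is looser on the model. It accepts a random effect of time as an alternative to the unstructured matrix, and time may be a category or a continuous covariate. It does not say how the choice is made. Neither text names a df method. Both note that rolling enrolment will leave some dyads with fewer observations.

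On follow-up, the Aim 4 procedures list full assessments at "12-month, 24-month and 36-month follow-ups for all participants". They also say that follow-up stops when the study ends, and that "participants enrolling after the 3/2/2023 IRB modification/approval are anticipated to end participation after the 18-month assessment". The description of the interventionist-satisfaction measure adds that "study funding ends in May 2025". The consent section for Aim 4, on re-consenting active participants who had signed before July 2022, says: "Trained research staff members will contact each of these participants (n=32), explain the changes".

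**The concern.** With categorical time and an unstructured covariance, the seven-visit test rests on many parameters, and those for months 24 to 36 are informed by a small early cohort. If the Wald F test treats these estimates as well determined, it rejects too often. A significant arm-by-time interaction could then be noise from the last visits.

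This matters because Hypotheses 2-4 have no other stated comparison of arms, and Hypothesis 1 relies on the same model beyond month 6. Having two permitted models with different error rates, and no rule for choosing between them, adds to the problem.

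**Working it through.** **Inputs from the documents**
- Dyads: "72 dyads randomized to the intervention and 53 dyads randomized to the control condition" (Subject Children, Section 2), so N = 125.
- Visits: 0, 6, 12, 18, 24, 30 and 36 months, seven in all. PARYC is in the annual battery and is collected at month 6. I take it as also collected at months 18 and 30.
- Funding ends May 2025; the project end date is 8/31/2025 (Project Information).
- 32 active participants had consented before July 2022.

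**Size of the model**
- Covariance parameters: 7 × 8 / 2 = 28.
- Interaction df: (2 − 1) × (7 − 1) = 6.

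**Who can reach month 36**
- May 2025 minus 36 months is May 2022; August 2025 minus 36 months is August 2022.
- The nearest count is the 32 consented before July 2022: 32 / 125 = 25.6%.
- Month 30 needs a baseline by about November 2022 on the funding date. Month 24 is limited to those enrolled before the 3/2/2023 modification. The documents give no count for either, so these are varied below.

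**False-positive rate**

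The plan's only figure is the nominal 5%. It gives no operating characteristics to reproduce. I simulated under the null: REML, unstructured 7 × 7 covariance, arm-by-visit means, 72/53 dyads, exchangeable correlation 0.6, normal data, monotone missingness unrelated to outcome, no coach effect. There were about 6,000 replicates per row (Monte Carlo SE about 0.3-0.5 points). Entries are the percentage of null data sets rejected at 5%.

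| Dyads at months 0/6/12/18/24/30/36 | Between-within df (123) | Residual df | Satterthwaite | Kenward-Roger |
|---|---|---|---|---|
| 125 at every visit | 6.1 | 6.9 | 6.1 | 5.2 |
| 125/125/125/125/90/60/32 | 10.1 | 11.0 | 9.4 | 5.8 |
| 125/125/125/125/64/48/32 | 10.7 | 11.8 | 9.9 | 6.0 |
| 125/115/108/100/55/42/32 | 11.0 | 11.9 | 10.1 | 5.7 |
| 125/115/100/85/40/32/32 | 12.5 | 13.4 | 11.2 | 5.8 |
| 125/125/125/125/32/32/32 | 13.3 | 14.3 | 11.9 | 6.3 |
| Attrition to 27 at month 36 | 12.9 | 13.9 | 12.0 | 6.7 |
| Attrition to 25 at month 36 | 13.8 | 14.8 | 12.4 | 6.5 |
| Attrition to 20 at month 36 | 17.0 | 18.0 | 15.3 | 7.1 |
| Four annual visits, 125/118/60/32 | 7.9 | 8.4 | 7.3 | 5.6 |

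With all 125 followed and Kenward-Roger, the nominal level is nearly recovered, which checks the method.

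Further runs agree:
- The 90/60/32 pattern gave 8.9-10.3% uncorrected.
- A 52/32/32 pattern at months 24/30/36 gave 12.6-14.0% uncorrected and 6.4-6.7% with Kenward-Roger, the latter under exchangeable 0.6 or AR(1) 0.8.
- With 25 dyads at month 36, some runs gave 14-16% uncorrected.
- Across patterns, Kenward-Roger did not exceed 7.2%.

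The SAP's alternative of continuous time with a random time effect gave 5.3% (1,200 replicates, some convergence warnings).

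**The case against.** The strongest reply has four parts.

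1. **The SAP permits a model that holds its level.** True, at about 5%. But the protocol fixes the categorical, unstructured model, the SAP still allows it, and no rule excludes it.

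2. **Silence on df does not mean that no correction will be used.** Also true. A reader might infer that the plan's real false-positive rate is 13-15%. The documents do not support that. It assumes an uncorrected test and one particular set of month-24 and month-30 counts, and the documents give neither. The 32 is likewise not a ceiling. It counts consents, not baselines; some of those dyads may be too late for May 2025 or may drop out, while a baseline in July or August 2022 could still reach month 36 by 8/31/2025.

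3. **The plan already limits follow-up.** A reader might infer a contradiction in scheduling months 24 and 36 for all participants. The same passage says that visits run only until the study ends and that later enrollees stop at 18 months, so rewording it would be largely cosmetic.

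4. **These are additional analyses, and the simulated model is not quite the planned one.** Both points stand. Nothing here touches the primary test at 6 months. Coach random effects and the stratification factors were not simulated, so the figures are approximate.

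**Conclusion.** The concern holds as a gap in specification. If the seven-visit, unstructured, categorical-time test is run without a small-sample correction, its false-positive rate would be roughly 9-15%, about two to three times nominal. If attrition leaves only 20 dyads at month 36, it would be 15-18%. Outcomes with four annual visits would be nearer 7-8%.

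That last figure assumes a baseline for every dyad. It therefore does not describe the child-administered language tests, whose baseline exists only for recruits after 3/2/2023.

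The range rests on about 32 dyads at month 36, assumed counts at months 24 and 30, assumed visit correlations, and missingness unrelated to outcome. The direction is secure: every staggered pattern examined was above nominal without correction, and Kenward-Roger removed most of the excess.

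**What to change.** In the protocol's Aim 4 data analyses and in the SAP:

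1. State that all longitudinal mixed models use the Kenward-Roger adjustment (DDFM=KR in SAS). This brings the seven-visit rate to about 6-7%.
2. Reconcile the two texts on one prespecified covariance and one time coding. For the child-administered language tests, no dyad is scheduled to have both a baseline and a month-24 or month-36 score, so the data cannot directly inform those unstructured covariances. The chosen structure should allow for this.
3. Report the number of dyads contributing at each visit, by arm.

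Restricting the test to months 0-18 is optional. With Kenward-Roger in both, simulated power for a constant 0.4 SD effect was 72% on four visits against 58% on seven (exchangeable), and 84% against 73% (AR(1)). An effect that grows with the annual repeat sessions was not examined and could favour keeping the late visits. The restriction should not be applied to the child-administered language tests: within months 0-18, month 12 is the only visit scheduled for all dyads, so no arm-by-time test common to all of them would remain.

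The cost is wording and one SAS option, with no new data. Longitudinal p-values become slightly less favourable.

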#### AIM 4 (EFFECTIVENESS)

Parent/caregiver and child participants in Aim 4 will engage in assessments scheduled every six months over approximately 3.25 years or until the study ends. In addition, participants randomized to the FCU-DHH condition will be offered the FCU-DHH intervention annually (described below). Participants randomized to the treatment-as-usual (TAU) control condition will complete assessments only throughout the course of the study. Research staff conducting data collection will be blinded to participants' random assignment (i.e., FCU-DHH vs. TAU).

(1) Procedures for Parent/Caregiver and Child Participants: In Aim 4, the primary parent/caregiver participant will complete the baseline assessments of parent- and child-level constructs either online via REDCap survey or by mailed paper forms (see Form M and description below). All parent/caregiver participants will also be offered the option to complete assessments with research staff over the phone to alleviate literacy or comprehension concerns. Four standardized videotaped parent/child tasks and a brief parent interview about how the child can hear in various situations will also be completed at baseline, with video captured remotely by HIPAA-compliant videoconferencing software. If parents do not have the capability to connect to videoconference sessions with equipment they own, the research staff will arrange a way to deliver equipment to the family (e.g., drop off equipment while waiting outside, or deliver by certified mail). For participants enrolled after the 3/2/2023 IRB modification/approval (in which participants will not complete any measures past 18-month assessments), the child participant will also participate in baseline speech, language, and hearing assessments with the trained data collector via HIPAA-compliant videoconferencing software (see description of measures, below, as well as Form M). Data collection for the parent/caregiver and/or the child will be separated into more than one session as needed to

prevent fatigue. No data collection will occur unless informed consent has been documented by REDCap or by a mailed copy of a signed paper consent form. Upon completion of baseline data collection, participants will be notified by mailed or emailed letter (according to the parent's preference) of their next steps in the study, depending on whether they were randomized to the FCU-DHH or TAU condition.

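### For CELF, PPVT-5 and BIT, no child is planned to have both a baseline and a 24- or 36-month score, so the arm-by-time interaction is a weak test of a language benefit established by 12 months and the unstructured covariance is only partly estimable.

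*Combined protocol and SAP*

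**What the plan says.** The protocol (Research Procedures, Aim 4 data analyses) fits linear mixed models with coach random effects to each outcome over time, names language development among those outcomes, and uses an unstructured within-subject covariance. It states that "trial arm, time (categorical), and their interaction will be used as predictors, with the interaction being of primary interest". The SAP is looser on form but the same on the test: "Fixed effects will include trial arm, time (categorical or continuous variable), and their interaction, with the interaction being of primary interest". It allows either a random time effect or an unstructured covariance. Both documents list baseline language development as a covariate for secondary models.

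The schedule for the child-administered tests is in the protocol's Aim 4 procedures:

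- CELF, PPVT-5 and BIT are given "At annual (12-month, 24-month, 36-month, and baseline for participants recruited after 3/2/2023) assessments".
- Payment terms confirm that there was no earlier baseline: "baseline assessments before 3/2/2023 (which do not include child language measures".
- For the later cohort, "participants will not complete any measures past 18-month assessments), the child participant will also participate in baseline speech, language, and hearing assessments". Another paragraph of the same section says only that this cohort is anticipated to end after 18 months.

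MacArthur-Bates, MAIS and the SALT-coded family interaction videos are scheduled at baseline and annually for all families.

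**The concern.** On these three tests, early-cohort children have at most 12, 24 and 36 months, and late-cohort children have baseline and 12 months. An arm-by-time interaction asks whether the arm difference changes between visits. In the early cohort, a benefit that is present at 12 months and then held does not change between the observed visits, so it falls in the arm main effect, which is not the named test. Only the late cohort can show a change from baseline to 12 months.

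The plan does not say how the missing baseline is handled, or whether baseline is a time level for these tests. Both documents note that some dyads will have fewer observations, but attribute this to rolling enrolment, not to a baseline that was never scheduled. At stake are a negative report on these tests when FCU-DHH children are ahead at every follow-up, a covariance that may fail to fit, and the loss of the early cohort from adjusted models if the baseline language covariate is taken from these tests.

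**Working it through.** **Inputs from the documents.** "72 dyads randomized to the intervention and 53 dyads randomized to the control condition" (125 in total); "All tests will be two-sided with a 5% significance level"; the visit schedule above. **Assumed, because not stated:** benefit in SD units, within-child correlation r (equal between all visits), and late-cohort share. No dropout is assumed, all early children reach 36 months, and coach clustering is ignored.

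**The plan's own figure.** The trial was sized on "the need to detect a medium-sized effect on the primary outcome (parenting behaviors", not on language. Taking medium as d = 0.5: SE = √(1/72 + 1/53) = 0.181, and power = Φ(0.5/0.181 − 1.96) = Φ(0.80) = 0.79. About 130 dyads would be needed for 80%. Power, ICC and dropout are not stated, so 125 can be neither confirmed nor refuted. Nothing below depends on it.

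**What can be estimated.** Four visits and two arms give 8 means. Each has data, and the fixed-effect information has rank 8 of 8. An unstructured 4×4 covariance has 4 variances + 6 covariances = 10 elements. The early cohort informs 6 (variances at 12, 24 and 36 months and their three covariances). The late cohort adds 2 (variance at 0, and cov(0,12)). That makes 8 of 10: cov(0,24) and cov(0,36) have no data. Changing those two values leaves the fixed-effect information unchanged (maximum difference 0.0).

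**Why the test is weak: one worked case.** Take 80 early, 45 late, r = 0.7, and v = 1/72 + 1/53 = 0.0328.

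- Change in arm difference from 0 to 12 months: variance = (1−r)²v + (1−r²)v·125/45 = 0.0029 + 0.0464 = 0.0494, SE 0.222. If every child had a baseline: 2(1−r)v = 0.0197, SE 0.140.
- Power for 0.5 SD on that single contrast: Φ(0.5/0.222 − 1.96) = 0.61. For the full 3-df interaction: 0.45.
- 12-month difference with baseline arm means set equal: var(d0) = (1−r²)v·125/45 + r²v = 0.0464 + 0.0161 = 0.0625; variance = v − (rv)²/var(d0) = 0.0328 − 0.0084 = 0.0243, SE 0.156, power Φ(0.5/0.156 − 1.96) = 0.89. The joint 3-df test of the 12-, 24- and 36-month differences: 0.82.

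**If baseline is not a time level.** The interaction contrasts are d24 − d12 and d36 − d12. With 0.5 at every visit both are 0, the noncentrality is 0, and power equals alpha, 5%.

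**Range.** Each multi-df power is the upper tail of a noncentral chi-square with λ = δ′V⁻¹δ beyond the 5% critical value (7.81 on 3 df). Here δ is the vector of tested contrasts and V their covariance matrix. With r = 0.6-0.7 and 25-60% late:

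| Benefit at 12/24/36 months (SD) | Planned 3-df interaction | Joint 3-df arm differences, equal baseline means | 12-month difference alone, equal baseline means |
|---|---|---|---|
| 0.5 / 0.5 / 0.5 | 26-67% | 80-86% | 84-93% |
| 0.25 / 0.50 / 0.75 | 56-82% | 75-96% | 31-41% |
| 0 / 0.25 / 0.50 | 39-76% | 43-82% | 5% (no effect at 12 months) |

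A single average of the three differences (weights 1/3 each, same matrices) has SE 0.155-0.171. The mean effect is 0.5 in rows one and two, giving 83-90% power. In row three it is (0 + 0.25 + 0.50)/3 = 0.25, giving Φ(0.25/0.171 − 1.96) to Φ(0.25/0.155 − 1.96), or 31-37%.

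With r = 0.5-0.8 and an early cohort of 32-100, the interaction's power for the constant benefit runs from 19% to 91%.

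**The case against.** The strongest reply is that this concerns three instruments in a secondary hypothesis and that the SAP already contains a way round the covariance problem. Much of that stands, and it limits four inferences that a reader might draw.

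- **That the planned model is not identified.** The documents do not support this. Every arm-by-time effect is estimable, only two covariances lack data, and the SAP's random time effect does not need them as free parameters.
- **That all of Hypothesis 4 is affected.** It is not. MacArthur-Bates, MAIS and SALT are scheduled at baseline and annually for every family.
- **That the interaction cannot see a 12-month benefit.** This is true only if baseline is left out as a time level, which neither document says. Otherwise the test is underpowered, not blind.
- **That the 12-month difference should simply replace the interaction.** Hypothesis 4 concerns language over time, and FCU-DHH is offered again after the 12- and 24-month assessments, so an accumulating benefit is plausible. Under the accumulating pattern in the table, the 12-month contrast alone is worse than the planned test.

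Nor does the point reach Hypothesis 1's primary test, which is an arm effect on PARYC at 6 months. What remains is that neither document acknowledges a baseline absent by cohort, and that the joint test of arm differences does better than the planned interaction under each benefit pattern tried.

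**Conclusion.** The concern holds for CELF, PPVT-5 and BIT only. As scheduled, no child has both a baseline and a 24- or 36-month score. The protocol's unstructured covariance is estimable in 8 of 10 elements. The interaction has about 26-67% power for a constant 0.5 SD benefit from 12 months, against 80-86% for the joint test with equal baseline means.

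The sizes depend on the assumed correlation, cohort split and effect pattern, none of which the documents give. Dropout, early children who do not reach 36 months, and coach clustering would generally lower the figures. The schedule gap and the two empty covariances do not depend on the power assumptions, but they do depend on the later cohort stopping at 18 months as planned. Severity is moderate: these are secondary analyses, and the primary analysis is untouched.

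**What to change.** In the SAP, for CELF, PPVT-5 and BIT:

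1. Keep baseline as a time level and constrain the arm means there to be equal. Families were randomised after completing baseline assessments, which justifies the constraint.
2. Make the arm differences at 12, 24 and 36 months the test of Hypothesis 4 on these tests, either jointly or as one pre-specified contrast such as their average. Report each visit's difference with a confidence interval. Do not rely on the 12-month contrast alone.
3. Name one estimable covariance structure, such as the random time effect that the SAP already allows.
4. Define the baseline language covariate from measures scheduled for every family at baseline (MacArthur-Bates, MAIS, SALT), so that the early cohort stays in the adjusted models.

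The cost is SAP text and analysis code, with no new data. It should be settled before unblinded analysis. The one downside is that a single average contrast has less power for a purely late effect; the joint test avoids this.
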